6. GENERAL STATISTICAL METHODS AND CONVENTIONS

6.1. General Methods

Summary statistics will be presented by treatment group, unless stated otherwise.

For continuous variables, descriptive statistics will include the number of patients with data to be summarized (n), mean, SD, median, minimum, and maximum.

For categorical/qualitative variables, descriptive statistics will include frequency counts and percentages. The total number of patients in a treatment group will be used as the denominator for percentage calculations, unless stated otherwise.

For time-to-event data with censoring, the Kaplan-Meier (KM) method will be used to summarize the data.

[figure not shown]

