6.2. Handling of Missing Data

6.2.1 Imputation of Missing Values

6WMT distance

If the patient is confirmed to have LOA (section 6.7), a value of 0 (zero) meters will be imputed for any missing values at the time or after the confirmation of LOA.

CCI

NSAA item and total score

If 4 or fewer of 17 NSAA items are missing, the score for the missing items will be assigned a value of zero. The NSAA total score will be calculated as the sum of the scores for the completed items. The total NSAA score will be treated as missing values when 5 or more items are missing.

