The duration of corticosteroid treatment, in months, will be calculated as (Day 1 – Date on which the patient started corticosteroid treatment + 1)/30.4375.

Corticosteroid Schedule

Corticosteroid schedules will include:

- Continuous (daily)
- Intermittent (includes all dosing schedules that do not require the patient to take at least one dose per day)

Non-Ambulatory Status and Loss of Ambulation (LOA)

The non-ambulatory status will be considered as “Yes” if all 3 conditions below are met:

- NSAA walk subscore as “0” (unable to achieve goal independently) on 2 consecutive days within a visit or NSAA was not done due to reason related to non-ambulation
- 6-minute walk test was not done with any reason related to permanent non-ambulation
- No later data showing this patient is still ambulatory. This is not required if non-ambulatory status occurs at the time of early withdrawal, or at the end of Week 96 assessment.

Note, when the NSAA or 6MWT is “Not Done” and the patient meets the non-ambulatory requirements above, a query will be issued to sites to confirm the permanence of non-ambulatory status. Prior to final database lock, the results of queries will be reviewed by Medical Director and Data Management and provided as documentation for non-ambulatory status determination.

Time to LOA is defined as the time from the initiation of eteplirsen for eteplirsen-treated patients, or Week 1 visit for untreated control patients to the first time of permanent non-ambulation. Patients who do not lose ambulation at the time of early withdrawal, or at the end of Week 96 assessment, whichever is earlier, the patient will be censored at the last time at which the patient is determined to be ambulatory.

NSAA and Total Score

The NSAA is a clinician-administered scale specifically designed for DMD patients that rates patient performance on various functional activities. Patients will be asked to perform 17 different functional activities including: stand, walk, stand up from chair, stand on one leg - right, stand on one leg - left, climb box step - right, climb box step - left, descend box step - right, descend box step - left, lift head, get to standing, rise from floor, stand on heels, jump, hop right leg, hop left leg, run 10 meters. Patients will be graded as follows

- 2 = achieves goal without any assistance;
- 1 = modified method but achieves goal independent of physical assistance from another person; and
- 0 = unable to achieve goal independently.

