A total score is derived by summing the scores for all the individual items. The total score can range from 0 (if all the activities are failed) to 34 (if all the activities are achieved). All items should be tested without thoracic braces or leg orthoses. The scale is generally completed in a maximum of 15 minutes.

Ability to Rise Independently from the Floor

The ability to rise independently from the floor (without external support) is indicated by a NSAA subscore greater than 0 (unable to achieve goal independently). To be considered as loss of ability to rise independently for any visit, the NSAA rise from floor subscore has to be zero on 2 consecutive days within a visit or NSAA missing due to reasons related to not able to accomplish the task.

The permanent loss of ability to rise independently from the floor to a patient is considered to have occurred at a specific visit if this visit as well as all subsequent visits, if any, all showed the loss of ability to rise independently from the floor.

[figure not shown]
For patients who were able to rise at baseline, time to the permanent loss of ability to rise independently from the floor is defined as the time from the initiation of eteplirsen for eteplirsen-treated patients, or Week 1 visit for untreated control patients to the first time of permanent loss of ability to rise independently; patients who do not experience permanent loss of ability to rise independently from the floor at the time of early withdrawal, or at the end of Week 96 assessment, whichever is earlier, the patient will be censored at the last time at which the patient is determined to be able to rise independently.

FVC% predicted, CCI

FVC% predicted will be calculated using the prediction equations described by Hankinson (Hankinson et al, (1999 [1]) based on patient's age, and height as following:

FVC% predicted = $100 * FVC / (b0 + b1 * \text{age} + b2 * \text{age}^2 + b3 * \text{height}^2)$, where b0, b1, b2, and b3 are coefficients).

CCI

Calculated Height

Calculated height will be used based on the following formula:

$$\text{Height (cm)} = 4.605U + 1.308A + 28.003$$

where U is the length of the ulna measured by using an anthropometer or calipers, and A is the patient's age in years.

CCI

C [REDACTED]
C [REDACTED]
I [REDACTED]
[REDACTED]
[REDACTED]
[REDACTED]

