7.8.1 Analyses of Primary Efficacy Endpoint

Missing 6MWT values will be imputed as specified in Section 6.2.1.

The primary efficacy endpoint, change from baseline at Week 96 in 6MWT distance, will be summarized as part of the by-visit summary for 6MWT.

Observed 6MWT distance and change from baseline will be summarized by treatment group and visit using descriptive statistics. A plot of the mean (+/- SE) of change from baseline in 6MWT distance will be generated.

In addition, summaries by Baseline 6MWT and Baseline age subgroups (see Section 6.5) may be presented for the primary efficacy set.

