Observed NSAA total score and change from Baseline will be summarized by treatment group and visit using descriptive statistics. A plot of the mean (+/- SE) of change from baseline in NSAA total score will be generated.

CCI

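### Patients who lose ambulation count as 0 m on the 6MWT but can drop out of the NSAA mean, so mean NSAA decline can be understated

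*SAP*

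**What the plan says.** SAP 6.2.1 holds both missing-data rules. For the 6MWT, once LOA is confirmed, "a value of 0 (zero) meters will be imputed for any missing values at the time or after the confirmation of LOA". SAP 7.8.1 applies this to the primary endpoint: "Missing 6MWT values will be imputed as specified in Section 6.2.1". For the NSAA, up to 4 missing items out of 17 are scored zero. Beyond that, "The total NSAA score will be treated as missing values when 5 or more items are missing". No reason for missingness is distinguished.

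SAP 6.7 defines LOA by three conditions. The first can be met by a walk item of 0 on both days or because "NSAA was not done due to reason related to non-ambulation". The second is a 6MWT not done because of permanent non-ambulation. For the separate rise-from-floor endpoint, SAP 6.7 counts as loss an "NSAA missing due to reasons related to not able to accomplish the task".

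Change in NSAA total is a secondary endpoint (SAP 3.1). SAP 7.8.2 states: "Observed NSAA total score and change from Baseline will be summarized by treatment group and visit using descriptive statistics". Under SAP 6.1 each summary shows the number of patients with data. Under SAP 7.8 the two test days are averaged, or one day is used if only one is available. Protocol 13.1 says missing values will not be imputed.

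**The concern.** The NSAA total is missing here because of the outcome being measured. The SAP treats that missingness as informative in three places: the LOA definition, the 6MWT rule and the rise-from-floor rule. It does not do so for the NSAA total.

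Two boys in the same functional state can therefore be handled differently. One who attempts and fails every item scores 0 and stays in the mean. One who is not tested because he cannot walk is left out.

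At stake are the NSAA mean and mean change by visit, and the plot of mean change. An affected patient contributes to visits before LOA and then disappears, so the NSAA curve can flatten as the weakest patients leave, while the 6MWT curve carries them at 0 m. A reader who sets the two curves side by side would not be looking at the same patients.

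**Working it through.** **Step 1: apply the rules to possible LOA records.** In each case the 6MWT was not done, as the LOA definition requires, so the distance is 0 m.

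- All 17 items attempted and failed: total 0, in the NSAA mean.
- Walk item 0 and up to 4 other items missing: total is the sum of the scored items, in the mean.
- Walk item 0 and 5 to 16 other items missing: no total, out of the mean.
- NSAA not done: 17 items missing, 17 ≥ 5, no total, out of the mean.

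A patient is lost at a visit only if neither test day yields a total. The gap thus covers the last two kinds of record, not every LOA patient.

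**Step 2: effect on the mean.** Let n be the patients with a total plus the affected patients, k the affected patients, B their mean baseline total, r the mean total they would have had at the visit, and d the mean decline in the others.

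- Observed-case mean change = −d
- Mean change over all n = [(n − k)(−d) + k(−(B − r))]/n
- Understatement of decline = (k/n)(B − r − d)

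This is positive only when B − r > d, that is, when the affected patients declined more than the others.

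**Step 3: inputs.** The plan gives no figure to reproduce. From the documents: n = 70, the planned treated patients with a baseline 6MWT of 300–450 m (SAP 4.2), and a scale of 0–34 (17 items × 2). Not in the documents, and assumed: k = 3, 7 or 14; B = 15–26; r = 0–3; d = 5–8.

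**Step 4: results.**

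- Smallest case, B = 15, r = 3, d = 8: B − r − d = 4. Understatement = 4k/70 = 0.17, 0.40 and 0.80 points for k = 3, 7 and 14.
- Largest case, B = 26, r = 0, d = 5: B − r − d = 21. Understatement = 21k/70 = 0.90, 2.10 and 4.20 points.
- Middle example, k = 7, B = 22, r = 2, d = 5: observed-case −5.0; over all 70, (63 × −5 + 7 × −20)/70 = −455/70 = −6.5.

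These ends follow from the assumed inputs and are not bounds. With k = 0 there is no effect.

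**Step 5: what a zero-filled summary would do.** Setting the missing totals to 0 overstates decline by (k/n)r. In the middle example it gives (63 × −5 + 7 × −22)/70 = −469/70 = −6.7, against −6.5 over all patients and −5.0 observed-case. When B − r > d, the zero-filled error is the smaller one if r < (B − d)/2. For B = 15 and d = 8 that threshold is 3.5. With k = 7, r = 3 gives errors of 0.30 (zero-filled) and 0.40 (observed-case), and r = 4 gives 0.40 and 0.30. Which summary is closer therefore depends on r, which is unknown.

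**The case against.** The asymmetry has a rationale. A permanently non-ambulatory boy walks 0 m, and one who cannot rise has lost rise; both values follow from the event. An NSAA total of 0 does not. The scale has 17 items, including lifting the head, and SAP 6.7 reserves 0 for failure on all of them. Leaving an untested total missing is also closer to the protocol's no-imputation statement. This stands, and it is why zero should not simply replace the present rule.

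The consequence is limited. The summary is descriptive, and SAP 6.3, 7.8 and 8.1 exclude comparison of the two groups. The n at each visit, the LOA counts, the Kaplan-Meier estimates and the listing let a reader see that patients were lost. This also stands, although none of these corrects the NSAA mean.

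Parts of the SAP cannot be seen. A blacked-out block precedes the NSAA rule in SAP 6.2.1, and the supplemental SAP on the external control is not available. The NSAA paragraph reads as complete, so a hidden exception is unlikely but cannot be excluded.

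A reader might infer that the SAP contradicts itself, or that the gap favours eteplirsen. The documents support neither. The rules concern different measures and can all be followed at once. The direction of any difference between groups depends on how often each group has such patients, which is not given.

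**Conclusion.** The point holds as a minor one. The stated NSAA rule removes patients from a named secondary summary because they lost ambulation, and mean decline is understated whenever they declined more than the patients observed. The size is (k/n)(B − r − d) and cannot be computed from the documents. The figure of about 0.4 to 2.1 points for 7 of 70 rests wholly on the assumed B, r, d and k. No between-group test in this SAP changes.

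A reader might go further and conclude that a zero total is the right value, or always the nearer one. That does not follow. It depends on how many points remain achievable after LOA, and the documents are silent on that.

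**What to change.** In SAP 6.2.1 and 7.8.2, add a second by-visit NSAA summary. In it, a total that is missing at or after confirmed LOA for a reason related to non-ambulation is set to 0, whether the NSAA was not done or 5 or more items are missing. Any observed total stays unchanged. Present it alongside the observed-case summary, and report the number of such patients by group and visit. List the rule in SAP 8.1 as a departure from the no-imputation statement in Protocol 13.1.

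The cost is a few sentences and minor programming, since SAP 6.7 already sends queries to the sites to confirm permanent non-ambulation when the NSAA or 6MWT was not done. Protocol 13.1 requires revisions to rest on blinded review, and an interim analysis has been done (SAP 4.4.1), so the change should be justified from the LOA definition and not from NSAA results.

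The drawback is that 0 is a floor and may overstate decline where items such as lifting the head are still achievable. The two summaries should be read together. They enclose the mean over all patients when the affected patients declined more than the others, but neither is a strict bound in every case.

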6.2.2 Imputation of Missing Laboratory Values

Laboratory data that are continuous in nature, but are less than the lower limit of quantitation or above the upper limit of quantitation will be imputed to the value of the lower or upper limit plus or minus 2 significant digits, respectively (eg, if the results of the continuous laboratory test is <20 or 2.0, a value of 19.99 or 1.99, respectively, will be assigned in computing summary statistics). Kidney injury molecule-1 (KIM-1) values that are reported as below the level of quantitation (<0.112) will deviate from the above rule and will be imputed as 0.099.

6.2.3 Handling of Incomplete Dates

An incomplete date will occur when the exact date an event occurred or ended cannot be obtained for a patient. Incomplete dates will be imputed as follows:

- For a partial or missing medication date, the medication will be classified as a concomitant medication unless the available part of the date indicates it is impossible for the drug to be concomitant. For example, if only the year for the stop date is available and the year is prior to the year of dosing, the medication will be classified as a prior medication.
- For a partial or missing AE onset date, the event will be classified as treatment emergent if the month and/or year of the onset date are on or after the initiation of eteplirsen and within 28 days of the last dose of eteplirsen for treated patients, or if the month and/or year of the onset date are on or after the date of the qualifying visit for untreated control patients.
- For the purpose of calculating the time since DMD diagnosis or duration of prior corticosteroid use, if the date of DMD diagnosis or the start date of corticosteroid use has a missing day but known month and year, then the 15th of the month will be used in the calculation. If only the year is known, December 31st of the recorded year will be used.

In all cases, the original missing or incomplete dates will be presented in the data listings.

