8. PATIENT POPULATION AND SELECTION

8.1. Inclusion Criteria

A patient must meet all of the following criteria to be eligible for this study.

- 1. Be a male with DMD and meet one of the following criteria:
 - Have an out-of-frame deletion that may be treated by exon 51 skipping (e.g., deletions of exons 45-50, 47-50, 48-50, 49-50, 50, 52, 52-63). These patients will be enrolled into the treated group.
 - Have an out-of-frame deletion that is not amenable to treatment by exon 51 skipping but is amenable to treatment by skipping other exons (i.e., whole exon deletions in which the reading frame may be restored by skipping 1 or 2 exons). These patients will be enrolled into the untreated control group.
- 2. Be 7 to 16 years of age, inclusive.
- 3. Have stable pulmonary function (FVC% of predicted ≥50% and not require nocturnal ventilation) that, in the Investigator's opinion, is unlikely to decompensate over the duration of the study.
- 4. Have intact right and left bicep muscles (the preferred biopsy site) or 2 alternative upper arm muscle groups.
- 5. Have been on a stable dose of oral corticosteroids for at least 24 weeks prior to Week 1 and the dose is expected to remain constant (except for modifications to accommodate changes in weight) throughout the study. Note: patients may be allowed to take other (non-RNA antisense or non-gene therapy) medication including angiotensin-converting enzyme (ACE) inhibitors, angiotensin receptor blocking agents (ARBs), β-blockers, potassium, and coenzyme Q, provided they have been on a stable dose for 24 weeks prior to Week 1 and the dose is expected to remain constant throughout the study.
- 6. Achieve a mean distance of 2 separate assessments on 2 consecutive days at the Screening and Baseline visits (prior to Week 1) ≥300 meters on the 6MWT with the 2 consecutive means being within 15% of each other, and with the Screening and Baseline 6MWT conducted 3 to 5 weeks apart. Personal assistance or use of any assistive devices for ambulation is not permitted during the 6MWT.
- 7. Male patients who are in the treated group and are post-pubertal and sexually active must agree to use, for the entire duration of the study and for 90 days post last dose, a male condom and the female sexual partner must also use a medically acceptable form of birth control (e.g., oral contraceptives).
- 8. Have a parent(s) or legal guardian(s) who is able to understand and comply with all the study requirements.

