6.7. Definitions and Terminology

Day 1

Day 1 will be defined as the date of the first eteplirsen dosing for eteplirsen-treated patients, or the Week 1 visit date for untreated control patients.

Study Day

Study day will be defined as Event Date – Day 1 + 1.

Duration on Study

Duration on study will be calculated as the duration in weeks from Day 1 to the date of study completion/discontinuation as recorded on the END OF STUDY eCRF (if completed) or the date of the last study assessment or procedure.

Duration on Eteplirsen

Duration on eteplirsen will be calculated as the duration in weeks from Day 1 to the date of the last eteplirsen administration as recorded on the STUDY DRUG ADMINISTRATION eCRF plus 6 days (ie, [last dose – first dose date + 1 + 6]/7).

Duration in weeks calculated above will be then categorized to 1 of the following intervals: <24, 24 to <48, 48 to <72, 72 to <96, or ≥ 96 .

Planned Dose and Overdose

The body weight-based planned dose was calculated based on most recent weight of previous visits. When calculating the planned dose, the body weight is rounded to a single decimal using conventional rounding rules. While in preparing actual dose, an unconventional rule is applied for calculating the volume of the concentrated drug (50 mg/mL) in milliliter. Any volume of 0.1 or above is rounded up (eg 25.14 mL is rounded up to 26 mL) and any volume below 0.1 is rounded down (eg 25.09 mL is round up to 25 mL). The overdose is defined as any actual dose $>10\%$ above the planned body weight-based dose.

Baseline Visit and Baseline value

Baseline visit will be considered the last visit prior to the initiation of eteplirsen for eteplirsen-treated patients, or the last visit on or before the Week 1 visit for untreated control patients. For any assessment that is taken on 2 consecutive days at baseline visit the base visit (ie, 6MWT, NSAA items and total score, FVC % predicted), the average value will be considered as the baseline value. If the assessment is taken or available only on 1 day at baseline visit, then the value on that day will be used as baseline value.

Change from Baseline

Change from Baseline will be calculated as follows:

$$\text{Change from Baseline} = \text{Post-Baseline Value} - \text{Baseline Value}$$

Percent Change from Baseline

Percent change from Baseline will be calculated as follows:

$$\text{Percent change from Baseline} = (\text{Change from Baseline} / \text{Baseline Value}) * 100$$

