Treatment-emergent Adverse Event

An AE will be considered treatment-emergent if it occurs in the time period starting with the initiation of the first dose of eteplirsen and ending 28 days after the last dose of eteplirsen for eteplirsen-treated patients, or on or after the Week 1 visit date for untreated control patients.

To define treatment emergence for AEs with missing onset or stop date or time, the following additional criteria will be used:

If both start and stop dates for a particular AE are missing, then the AE is considered treatment emergent.

- If onset date for a particular AE is missing, and stop dates falls after the first date/time, then that AE is considered treatment emergent.

- If onset date for a particular AE is the same as the first dose date and the start times missing, and stop dates falls after the first date/time, then that AE is considered treatment emergent.

Treatment-related Adverse Event

A treatment-related AE is any AE reported on the ADVERSE EVENTS eCRF that is marked as definitely related, or probably/possibly related to study drug.

Treatment-emergent Laboratory Abnormality

A treatment-emergent laboratory abnormality will be defined as any laboratory abnormality occurring or worsening after the initiation of eteplirsen dosing and within 28 days of the last dose of eteplirsen for eteplirsen-treated patients or occurring or worsening on or after the Week 1 visit for untreated control patients.

Prior Medication

A prior medication will be any medication taken and completed prior to the first dose of eteplirsen for eteplirsen-treated patients, or before the Week 1 visit for untreated control patients.

Concomitant Medication

A concomitant medication will be any medication that is taken in the time period starting with the initiation of the first dose of eteplirsen dosing and ending 28 days after the last dose of eteplirsen for eteplirsen-treated patients, or on or after the Week 1 visit for untreated control patients.

Previous Drisapersen Exposure Status

A patient will be considered as having previous exposure to drisapersen if he had taken any drisapersen prior to Day 1 in this study (value=Yes); otherwise a patient will be considered as not having a previous exposure to drisapersen (value=No).

Time Since DMD Diagnosis

The time since DMD diagnosis, in months, will be calculated as (Day 1 – Date of DMD diagnosis + 1)/30.4375.

Duration of Corticosteroid Treatment

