7.2. Demographics and Baseline Characteristics

Demographic and baseline characteristics will be summarized by treatment group for the safety set. These variables will include age (years), race, ethnicity, Baseline height (cm), Baseline weight (kg), Baseline body mass index (kg/m²), time since DMD diagnosis (months) at Baseline, mutation type(s), previous drisapersen exposure status, corticosteroid medication, corticosteroid schedule, duration of prior corticosteroid use at Baseline, prior physiotherapeutic interventions (within 3 months prior to the study: Yes vs No), and Baseline 6MWT distance.

An additional summary will be produced for the primary efficacy set and for the subset of patients with Baseline 6MWT > 450 meters.

Patient-level demographic data and baseline characteristics will be presented in data listings.

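### Year-only diagnosis and steroid-start dates are set to 31 December, so the affected baseline durations can only be understated (by about 6 months on average if true dates are uniform over the year) and are occasionally negative

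*SAP*

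**What the plan says.** SAP 6.2.3 has one bullet for incomplete dates of DMD diagnosis and of the start of corticosteroid use. If such a date "has a missing day but known month and year, then the 15th of the month will be used in the calculation". The next sentence covers a date with neither day nor month: "If only the year is known, December 31st of the recorded year will be used". The section ends by requiring that the dates be listed as originally recorded.

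SAP 6.7 defines the two derived variables. For diagnosis: "The time since DMD diagnosis, in months, will be calculated as (Day 1 – Date of DMD diagnosis + 1)/30.4375". Prior corticosteroid duration uses the same expression with the steroid start date. The anchor is also in SAP 6.7: "Day 1 will be defined as the date of the first eteplirsen dosing for eteplirsen-treated patients, or the Week 1 visit date for untreated control" boys. Neither section caps an imputed date at Day 1 or sets a floor for the result.

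The variables are used in SAP 7.2: "Demographic and baseline characteristics will be summarized by treatment group for the safety set", with further summaries for the primary efficacy set and for boys with a baseline 6MWT above 450 meters. Both durations are among the listed characteristics.

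Protocol 8.1, inclusion criterion 5, bears on the steroid variable. A boy must "Have been on a stable dose of oral corticosteroids for at least 24 weeks prior to Week 1".

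**The concern.** The bullet treats two similar gaps in opposite ways. A missing day goes to a near-central value, so errors roughly cancel. A missing month goes to the end of the possible range, so every error has the same sign. The SAP gives no reason for the difference, and a descriptive baseline variable has no conservative direction that would supply one.

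The baseline table matters here because the arms are assigned by genotype, not randomized (SAP 4.3), and the SAP itself cites differences between the two populations (SAP 8.1). A reader will use that table to judge how alike the arms are. Protocol 13.2 names the use of steroids among the factors affecting 6MWT decline, so steroid history is a characteristic that such a reader will look at. A rule that shifts it in one direction, and that can print negative durations or durations shorter than eligibility implies, weakens the table for no gain.

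**Working it through.** The plan gives no figure for this error, so there is none to reproduce.

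**Inputs from the documents.** Year-only date = 31 December (SAP 6.2.3); duration = (Day 1 − date + 1)/30.4375 months (SAP 6.7); at least 24 weeks = 168 days = 168/30.4375 = 5.5 months on a stable steroid dose before Week 1 (Protocol 8.1).

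**Assumptions.** The documents give neither the distribution of true dates within the year nor the share of year-only records. I take a uniform distribution as the base case, with skewed alternatives, and shares of 5% to 50%.

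**Error per year-only record.** Derived minus true duration = (true date − imputed date)/30.4375. With 31 December imputed this is never positive.

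| True dates within the year | Mean understatement, months |
|---|---|
| Uniform, 365-day year | 182/30.4375 = 5.98 (range 0 to 364/30.4375 = 11.96) |
| Uniform, 366-day year | 182.5/30.4375 = 6.00 (range 0 to 365/30.4375 = 11.99) |
| Clustered late, Beta(2,1) | (1/3 × 364)/30.4375 = 4.0 |
| Clustered early, Beta(1,2) | (2/3 × 364)/30.4375 = 8.0 |

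For comparison, the 15th-of-month rule has a mean error of about 0.7 days.

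**Shift in a group mean.** Share of year-only records × 5.98 months: 0.3 at 5%, 0.6 at 10%, 1.2 at 20%, 3.0 at 50%.

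**Negative values.** With the recorded year equal to the year of Day 1, the numerator is Day 1 − 31 December + 1. It is −1 on 29 December, 0 on 30 December and 1 on 31 December, so every Day 1 up to 29 December gives a negative duration.
- For steroids, 24 weeks of prior use make a same-year start possible only from 1 January + 168 days = 18 June (17 June in a leap year). On 18 June the derived value is (169 − 365 + 1)/30.4375 = −6.4 months.
- Example: start 1 February, Day 1 on 1 September (days 32 and 244 of the year). True: (244 − 32 + 1)/30.4375 = 7.0 months. Derived: (244 − 365 + 1)/30.4375 = −3.9 months.

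**Values below 24 weeks.** With a start recorded in the previous year, the derived duration in days is the day-of-year of Day 1 plus 1. It is under 168 when the day-of-year is 166 or less, that is, up to 15 June (14 June in a leap year). Day 1 on 1 March gives 61/30.4375 = 2.0 months, although an eligible boy has at least 5.5.

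**Mid-year instead (1 July).** Uniform true dates: mean error +0.02 to +0.03 months, range about −6.0 to +6.0, mean absolute error 3.0 instead of 6.0 months. For a previous-year start, even Day 1 on 1 January gives 184 + 1 = 185 days, so no such record falls below 168. Same-year records stay crude: a Day 1 up to 29 June is still negative without a cap, and the 1 September example gives 63/30.4375 = 2.1 months against a true 7.0.

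**The case against.** The strongest reply is that little depends on this. The variables are descriptive. The SAP makes no comparison between the arms (6.3, 7.8, 8.1) and no covariate adjustment (6.4), and neither variable is a listed subgroup factor (6.5). The original partial dates are listed, and glucocorticoids have their own listing (7.3), so affected records can be traced. All of that stands and keeps the point minor. It does not make the table right, because a listing does not correct a summary mean.

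Negative values should also be uncommon. Protocol 5.1 puts diagnosis usually at 3 to 5 years of age, while entry is at 7 to 16. A same-year steroid start in an eligible boy needs a Day 1 from mid-June onward. That stands too.

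Four stronger readings are tempting, and the documents do not support them.
- A reader might infer that both durations are 6 months too short for everyone. The figure applies only to year-only records and rests on the uniform assumption.
- A reader might infer that the rule contradicts inclusion criterion 5. It does not: sites judge eligibility at Screening and Baseline and reconfirm it at Week 1 (Protocol Section 2), and no text uses the derived duration for that purpose. The derived value can merely look inconsistent with it.
- A reader might infer that the arms are biased differently. That is possible if year-only recording differs by arm, but nothing in the documents shows that it does.
- A reader might infer that efficacy results are affected. No efficacy analysis in the readable SAP uses these variables. Whether the external-control comparison will use them depends on the supplemental SAP announced in SAP 4.4.2, which is not available here.

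**Conclusion.** The point holds as a minor flaw in a stated rule. The direction is certain and needs no assumption: no year-only record can be overstated. The size rests on the unknown timing of true dates, and its effect on a group mean also on the unknown share of year-only records. At shares of 5% to 20% under the uniform assumption the group mean moves by 0.3 to 1.2 months. Negative durations follow from the formula for same-year records, and steroid durations below 24 weeks for previous-year starts with Day 1 before mid-June. The consequence ends at the baseline summaries by arm.

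**What to change.** In SAP 6.2.3, replace 31 December with a mid-year date such as 1 July for year-only dates, in line with the 15th-of-month rule. Add that an imputed date falling after Day 1 is set to Day 1, for both variables. The cap is needed because mid-year alone leaves some same-year records negative; with it the smallest derived value is one day.

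Do not set steroid start to 24 weeks before Week 1. SAP 7.6 expects inclusion and exclusion deviations, and that rule would give a boy enrolled in deviation a duration that appears compliant. For a same-year start with Day 1 before mid-June it would also move the date out of the recorded year.

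It would help to footnote the baseline table with the number of year-only dates per arm, so that readers can apply the shift themselves.

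The cost is two or three sentences in the SAP and a small change to the derivation program. No new data are needed.
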